5.2 SECONDARY ENDPOINT(S)

[figure not shown]
5.2.1 Key secondary endpoint(s)

[figure not shown]
There were no key secondary endpoints for this study.

5.2.2 Secondary endpoint(s)

The following secondary endpoints related to safety and PK, were specified:

- Exposure measures (AUC_{0-tz}) after the first dose
- Disposition kinetic measures ($t_{1/2}$) after the first dose
- Drug related AEs leading to dose reduction or discontinuation during the treatment period

6. GENERAL ANALYSIS DEFINITIONS

6.1 TREATMENT(S)

The starting dose of the study is BI 836880 40mg every three weeks, and dose escalation decision will be made by Data Safety Board (DSB).

The following treatment period will be defined:

- Screening: from the date of informed consent to the date of first study medication intake -1 day.
- On-treatment: from the date of first infusion of study drug to the date of last study drug administration + 42 days, i.e., actual on-treatment period + residual effect period (REP).
- Post-study: from the last day of on-treatment period + 1 day onwards

6.2 IMPORTANT PROTOCOL VIOLATIONS

A protocol violation (PV) is important if it affects the rights or safety of the study patients, or if it can potentially influence the primary outcome measurements in a non-negligible way. Patients with important PVs that could potentially impact the evaluation of the primary endpoint(s) will be excluded.

A list of important PVs is given in Table 6.2: 1 below. Important PVs will be reviewed at Medical Quality Review Meetings (MQRMs) conducted periodically during the trial. A list of protocol deviations will be discussed at the blinded report planning meetings (BRPMs).

If the data show other important PVs, this table will be supplemented accordingly at MQRMs or BRPMs or through team review of the manual PV log. The decision whether a patient will be excluded from the analysis will be made at the final BRPM prior to DBL.

Table 6:2 1 Important protocol violations

| Category / Code | Description | Requirements | Excluded from |
|-----------------|--|---|---------------|
| A | Entrance criteria not met | | |
| A1 | Inclusion criteria not met | | |
| A1.1 | Requirements on age or birth control not met | Inclusion criteria 1 or 8 | None |
| A1.2 | Disease severity not met | Inclusion criteria 2 | None |
| A1.3 | Adequate health condition not met | Inclusion criteria 3, 4, 6, or 7 | None |
| A2 | Exclusion criteria not met | | |
| A2.1 | Hypersensitivity to the trial drug | Exclusion criteria 1 | None |
| A2.2 | Previous anti-cancer therapy washout period not met | Exclusion criteria 2 | None |
| A2.3 | Clinically relevant concomitant or history of disease, pre-existing conditions | Exclusion criteria 3, 4, 5, 6, 7, 8, 9, 10, or 11 | None |

Table 6.2: 1 Important protocol violations (cont.)

| Category / Code | Description | Requirements | Excluded from |
|-----------------|---|---|---------------|
| A | Entrance criteria not met | | |
| A2.4 | Under judicial protection and legally institutionalized | Exclusion criteria 12 | None |
| A2.5 | Requirement of adherence to protocol not met | Exclusion criteria 13 | None |
| A2.6 | Pregnancy / breast feeding related | Exclusion criteria 14 | None |
| B | Informed consent | | |
| B1 | Informed consent not available/not done | Informed consent date missing | All |
| B2 | Informed consent too late | Informed consent date was after screening visit date | None |
| C | Trial medication and randomisation | | |
| C1 | Incorrect trial medication taken | To be determined on a case by case basis. Listing will be created and decision will be made at MQRM / BRPM, e.g., incorrect dose taken, dose in course 1 not following dose escalation scheme, overdose, use of expired medication etc. | None |
| C3 | Non-compliance | Study drug not taken according to protocol. To be determined on a case by case basis. Listing will be created and decision will be made at MQRM / BRPM e.g., outside of dosing schedule window, unreasonable drug administration time, etc. | None |
| C5 | Re-treatment criteria not met | Re-treatment criteria was not met according to CTP section 4.1.4 | None |
| D | Concomitant medication | | |
| D2 | Prohibited medication use | Refer to CTP section 4.2.2.1. | None |
| Z | Other | | |
| Z3 | Missing critical safety information in cycle 1 | Essential safety information for the evaluation of DLT is missing | None |

6.3 PATIENT SETS ANALYSED

Treated set:

This patient set includes all patients enrolled in the trial who were documented to have taken at least one dose of study medication.

Dose finding cohort treated set:

This patient set includes all patients enrolled in dose finding and confirmation of MTD cohort of the trial who were documented to have taken at least one dose of study medication and were evaluable for the MTD determination.

MTD Expansion cohort treated set:

[figure not shown]
This patient set includes all patients enrolled in expansion cohort of the trial who were documented to have taken at least one dose of study medication.

Tumor type expansion treated cohort set (if applicable)

This patient set includes all patients with selected tumor type enrolled in expansion cohort of the trial who were documented to have taken at least one dose of study medication.

PK analysis set (PKS):

This patient set includes all patients with at least one PK sample taken.

[figure not shown]

6.5 POOLING OF CENTRES

This section is not applicable.

6.6 HANDLING OF MISSING DATA AND OUTLIERS

Missing or incomplete AE dates are imputed according to BI standards (see “Handling of missing and incomplete AE dates”) (3). Missing data and outliers of PK data are handled according to (2). Please refer to section 7.5 of the CTP for more details.

6.7 BASELINE, TIME WINDOWS AND CALCULATED VISITS

Baseline values will be the measurements taken most recently prior to first administration of study drug (same dates are allowed). If not available, then the values reported at the screening visit will be considered. For lab values, baseline is the one observed closest but prior to or on the first day of drug infusion.

Time windows and visits will be calculated to determine the planned day of tumour measurement and response status, based on the protocol-specified tumour imaging schedule. Imaging data will be displayed as screening, Week 6, 12, 18... etc. The number of weeks will be calculated using their relative day (from start of treatment) using a ±3 week window (images taken in the first 3 weeks from start of treatment will be assigned to Week 6). . Imaging not older than 28 days at start of treatment will suffice as screening images and do not need to be repeated.

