5.3.4 Vital Signs

Vital signs (blood pressure, heart rate and body temperature) will be recorded at every visit indicated in the FC.

At days of administration blood pressure and heart rate will be evaluated at two time points:

1. pre-dose (-60 min. to -5 min.),
2. shortly before the end of the infusion.

In case of an infusion-related reaction, the Investigator should decide whether to intensify or prolong monitoring of vital signs of the patient.

Blood pressure

Systolic and diastolic blood pressure as well as pulse rate (electronically or by palpation, count for 1 minute) will be measured after 5 minutes of rest in the seated position. The blood pressure measurement should be performed three times at each time point and the values of these measurements will be entered in the eCRF. Further details on the procedure for blood pressure measurements are given in [Appendix 10.2](#).

Body temperature

Whenever possible the same method should be used for body temperature measurement in one patient. All methods used should deliver valid and reproducible results according to

common clinical practice. Acceptable methods could be, but are not limited to: oral, rectal measurement with thermometer (digital, mercury or other fluid). Not acceptable/preferred methods include: IR-measurement in ear, forehead or temple.

Body temperature measurements $\geq 38^{\circ}\text{C}$ must be re-assesed after 1 hour, especially in cases suspective for febrile neutropenia (see CTCAE v. 4.03).

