5.3.5 Safety laboratory parameters

Blood and urine samples for assessment of general safety laboratory examinations have to be collected at the time points specified in the [Flow Chart](#), but should be more frequent in case of relevant findings, e.g. in case of grade 4 neutropenia, as any non-proven recovery within 7 days will be counted as DLT or proteinuria, for which determination of CTCAE grade 2 vs. grade 3 need to be done by quantitative measurement. Laboratory values planned for V1d1 (=day of administration) must be available before start of infusion in order to evaluate eligibility of patient to receive treatment. Therefore it's possible to take blood sample a valuable time ahead (usually the day before treatment). Safety laboratory examinations will include hematology, biochemistry, coagulation and urine analysis:

Hematology	Hemoglobin, white blood cell count (WBC) with differential, platelets (PLT)
Biochemistry	Glucose, sodium, potassium, calcium, magnesium, inorganic phosphate, creatinine, AST, ALT, alkaline phosphatase (AP), lactate dehydrogenase (LDH), bilirubin, urea, total protein, albumin, uric acid, CK, CK-MB
	Serum immunoglobulin levels (IgG, IgM, IgA; IgE) and direct antiglobulin test have to be measured at Screening and at occurrence of infusion related reactions.
Coagulation	Activated partial thromboplastin time (aPTT), prothrombin time (PT) or international normalised ratio (INR) where indicated (e.g. treatment with vitamin K antagonists)
Urine	pH, glucose, erythrocytes, leukocytes, protein, nitrite will be analysed primarily qualitatively by dipstick.. In case of clinically relevant findings, further evaluation should be performed and the findings documented. A positive urine dipstick for protein of $\geq 2+$ (CTCAE gr 2) has to be followed by a determination of the ratio of urine protein to creatinine (UPCR) in a morning spot urine sample. In case of a ratio ≥ 0.5 , a 24 hour urine collection for protein loss has to be performed. The 24 hour urine collection will be repeated every time the UPCR ratio is ≥ 0.5 as often as clinically indicated.
Pregnancy test	A serum pregnancy test needs to be obtained at the time

points indicated in the [Flow Chart](#) in patients of childbearing potential.

In case an administration is delayed due to an AE, the patient should visit the site at least once a week for assessment of safety laboratory and AEs. More frequent visits may be appropriate as assessed by the Investigator.

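### SAP 6.7's calendar-day lab baseline lets a day-1 infusion-reaction sample replace screening as the baseline for immunoglobulins and the direct antiglobulin test

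*SAP*

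**What the plan says.** SAP section 6.7 gives two baseline rules. The general one reads "Baseline values will be the measurements taken most recently prior to first administration of study drug (same dates are allowed"), followed by a fallback: "If not available, then the values reported at the screening visit will be considered". Laboratory values then get their own sentence: "For lab values, baseline is the one observed closest but prior to or on the first day of drug infusion". That sentence works by date. It contains no clock-time condition and does not mention unscheduled samples.

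Protocol section 5.3.5 lists serum immunoglobulins and the direct antiglobulin test among the safety laboratory parameters, but says that they "have to be measured at Screening and at occurrence of infusion related reactions". No pre-dose sample is planned for them on day 1. For the planned day-1 safety laboratory tests, the same section requires results before the infusion begins, and for that reason "it's possible to take blood sample a valuable time ahead (usually the day before treatment").

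SAP section 7.8.2 plans descriptive statistics with change from baseline for all converted laboratory values, and frequency tables of transitions relative to the reference range. Protocol section 7.5 replaces a missing baseline laboratory value by the screening value.

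**The concern.** A baseline should describe the patient before exposure. For immunoglobulins and the antiglobulin test, the only day-1 sample that the protocol requires is one prompted by a reaction, so it is taken after the infusion has started. The laboratory sentence in SAP 6.7 admits that sample and prefers it to screening, because it is closer in date.

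These tests are repeated at a reaction so that the result can be set against the pre-exposure state. The rule removes that comparison in the patients for whom the repeat was ordered. A newly positive antiglobulin test would count as the patient's starting state. If the patient reacted again later, the second sample would be compared with the first reaction. The protocol's benefit-risk section (2.3) promises special attention to immunogenic side effects, so this is a poor place for a self-cancelling comparison.

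**Working it through.** The plan states no figure to reproduce. The check applies the written rule to the sampling patterns that the protocol allows.

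**Inputs**
- Laboratory baseline: closest value dated on or before the day of first infusion (SAP 6.7).
- Screening window: day -21 to day -1 (protocol Flow Chart). A day-1 sample is therefore always closer in date than screening.
- Immunoglobulins and antiglobulin test: screening and reaction only (protocol 5.3.5).
- Planned day-1 laboratory results: available before the infusion (protocol 5.3.5).
- Expected infusion time: 90 minutes (protocol 4.1.4). A reaction during the first infusion, if sampled at once, will ordinarily carry the day-1 date.

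**Rules compared**
- SAP rule: baseline B is the latest value with date ≤ day 1.
- Pre-infusion rule: B is the latest value collected before the start of the first infusion.
- Change at reaction = reaction value − B.

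**Cases.** The IgE values (arbitrary units) and the planned-test value are invented to show the mechanism.

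| Case | SAP rule | Pre-infusion rule |
|---|---|---|
| 1. Screening IgE 100; reaction sample 160, day 1, 0.5 h after start | B = 160; change 160 − 160 = 0 | B = 100; change 160 − 100 = +60 |
| 2. As case 1, but reaction sample dated day 2 | B = 100; change +60 | B = 100; change +60 |
| 3. Planned test, day 1, 2 h before start, value 105; no later day-1 sample | B = 105 | B = 105 |
| 4. Planned test drawn the day before; unscheduled sample on day 1 after start | B = unscheduled sample | B = planned sample |

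Case 1 is the error. Cases 2 and 3 show where the rule does no harm. Case 4 is the route by which another laboratory test could be affected. If the planned and the unscheduled samples both carry the day-1 date, they tie, and SAP 6.7 gives no tie-break.

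**Fallbacks.** The screening fallback in SAP 6.7 and the imputation in protocol 7.5 both apply only when a baseline value is missing. In case 1 a qualifying value exists, so neither is reached.

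**How many patients.** The number is N × p × q, where p is the first-infusion reaction rate and q is the share of reactions sampled on day 1. The documents give neither p nor q. Setting q = 1 as an upper limit and assuming p = 5%, 10% or 30%:
- of about 40 dose-finding patients: 40 × 0.05 = 2, 40 × 0.10 = 4, 40 × 0.30 = 12;
- of about 80 in total: 80 × 0.05 = 4, 80 × 0.10 = 8, 80 × 0.30 = 24.

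The 30% is the only reaction frequency that the protocol names (section 4.1.4). It is a trigger for general premedication among treated patients, not a forecast of first-infusion reactions. The range shows scale only.

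**The case against.** The strongest reply is that a pre-dose baseline was plainly intended. The general sentence says so, and a programmer might apply it to laboratory data. SAP 7.8.2 also refers to a sponsor standard for laboratory data that is not among the documents and may settle the matter. This makes it uncertain what the program will do, but the written rule is unchanged: laboratory values have a separate, more specific sentence, and it admits any value from the day of infusion.

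A second reply is that little depends on these tests. They are not among the parameters on which SAP 7.8.2 focuses. Its change-from-baseline summaries are by visit, while issues that need an extra visit go on a separate unscheduled-visit page (protocol 6.1). Infusion reactions are also captured as graded adverse events regardless of any laboratory baseline. All of this stands. It limits the importance of the point, and the documents do not show which table would display the zero. The baseline still enters the change and transition outputs planned for all converted values.

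A reader might infer that blood pressure and ECG share the problem, since a second reading is taken "shortly before the end of the infusion" on dosing days. The documents do not support this. Those measurements fall under the general rule, which requires a value before first administration; its parenthesis is naturally read as admitting same-day pre-dose values. Appendix 10.4 gives the two readings distinct planned times (-0:05 and 1:30), and protocol 7.3.4 compares vital signs with findings before treatment.

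**Conclusion.** The point holds for laboratory data. As written, SAP 6.7 makes a day-1 reaction sample the baseline for immunoglobulins and the direct antiglobulin test, and the comparison at that reaction is then null by construction. The same can happen to any other laboratory test with an unscheduled day-1 sample drawn after the infusion starts. This assumes that the sample carries the day-1 date and that the laboratory sentence is programmed literally.

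Three wider readings should be resisted:
- Not every patient with a first-infusion reaction is affected. A sample dated day 2 or later leaves screening as baseline.
- Routine laboratory shifts are not generally suppressed. Planned day-1 values precede the infusion, and nothing in the documents shows that immunoglobulins or the antiglobulin test receive a CTC grade.
- The MTD is not at risk. It rests on DLT counts, which do not use this baseline rule. The secondary endpoints (PK, and drug-related adverse events leading to dose reduction or discontinuation) do not use it either.

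The number of patients is unknown and the consequence is limited to descriptive laboratory tables. It is still worth correcting, because a stated rule yields a wrong reference value and the remedy is small.

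**What to change.** In SAP 6.7, replace the laboratory sentence with text to this effect: *For laboratory values, baseline is the last value collected before the start of the first infusion. Samples taken on day 1 after that start, including those prompted by an infusion-related reaction, are not eligible. For immunoglobulins and the direct antiglobulin test, baseline is the screening value.*

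The documents do not say that clock time is recorded for safety laboratory samples. The SAP should therefore add that, where it is missing, eligibility is decided by planned time point or visit label.

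Optionally, clarify in the general sentence that the allowance for equal dates means same-day values taken before dosing.

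The cost is a short SAP text change and one programming condition. No new data are needed, since screening and planned pre-dose values are already collected. The one practical check is whether visit labels in the database identify unscheduled day-1 samples reliably.

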7. PLANNED ANALYSIS

For End-Of-Text (EoT) tables, the set of summary statistics is: N / Mean / SD / Min / Q1 (lower quartile) / Median / Q3 (upper quartile) / Max.

Tabulations of frequencies for categorical data will include all possible categories and will display the number of observations in a category as well as the percentage (%) relative to the respective treatment group (unless otherwise specified, all patients in the respective patient set whether they have non-missing values or not). Percentages will be rounded to one decimal place. The category missing will be displayed only if there are actually missing values.

7.1 DEMOGRAPHIC AND OTHER BASELINE CHARACTERISTICS

Only descriptive statistics are planned for this section of the report.

7.2 CONCOMITANT DISEASES AND MEDICATION

Only descriptive statistics are planned for this section of the report.

7.3 TREATMENT COMPLIANCE

Only descriptive statistics are planned for this section of the report.

Compliance will be calculated for subjects having attended the visit. A subject is considered having attended the visit if the indicated visit is captured in the eCRF database. In particular, if a subject attended the visit, but is not treated at the visit, the compliance of this visit is considered as 0%.

Compliance with trial medication will be based on the drug infusion/administered eCRF data and calculated as amount of drug infused/administered divided by the amount of drug to be infused/administered expressed as a percentage, see calculations below.

“Per Visit” Compliance to trial medication will be calculated as follows:

$$\frac{(\text{Amount of drug infused/administered at Visit X(n)})}{(\text{Amount of drug planned to be infused/administered at Visit X(n)})} \times 100$$

Overall Compliance for first treatment cycle of all patients will be calculated as mean of “per visit” compliance at visit Day 1.

Overall Compliance for second treatment cycle onwards (from Day 22 onwards) of all patients will be calculated as mean of “per visit” compliance at each visit. Overall Compliance to trial medication will be calculated as mean of the “per visit” compliance.

The compliance will be based on the total volume infused in mL (eCRF data) compared to total volume prepared (eCRF data).

7.4 PRIMARY ENDPOINT(S)

The primary endpoint is to assess the MTD based on the number of patients presenting DLTs during the MTD evaluation period. The primary analysis is for the determination of the MTD. The purpose of this analysis is to summarize and document the data that led to the selection of the MTD. Therefore, an overall summary of DLTs (see CTP section 5.3.1 for the definition of DLTs) which occurred during the MTD evaluation period will be provided for each dose cohort from the dose finding cohort treated set. Patients, if any, who did not complete the MTD evaluation period for reasons other than DLT will be excluded from the analysis of the primary endpoint.

A summary of the number of patients with DLTs overall in any course will be also given by initial treatment and displayed in a similar format to the summary of DLTs occurring in the MTD evaluation period.

The analysis of the MTD is based on a Bayesian logistic regression model (BLRM) guided by the escalation with overdose control principle. The MTD is defined as the highest dose for a given schedule that is expected to cause less than 25% risk of the true DLT rate being above or equal to 33% during the MTD evaluation period. Estimation of the MTD during the dose escalation phase of the study will be based upon the estimation of the posterior probability of the incidence of DLT in toxicity categories during the MTD evaluation period for all evaluable patients. The model to be used is specified in CTP section 7.

The posterior probabilities that the toxicity rates of each dose level fall into the categories specified in CTP section 7 will be displayed.

[figure not shown]
